Appendix D: Hematologic Adverse Event Grading Scheme (Hallek 2008)

An evaluation of the hematologic toxicity in patients with advanced CLL/SLL must consider the high frequency of marrow involvement and previous exposure to chemotherapy with consequent medullary compromise at the initiation of therapy. The standard hematologic grading system for solid tumors cannot, therefore, be directly applied. A substantial proportion of patients would be considered to have Grade 2 to 4 hematologic toxicity before any therapy is given. Therefore, the following modified schema will be used to quantitate hematologic deterioration in patients with CLL/SLL.

Hematologic Grading Scheme

Decrease in Platelets or Hgb (Nadir) from Pre-treatment Value, %	ANC/μL (nadir)^c	Toxicity Grade
0 - 10% ^a	≥ 2000	0
11 - 24% ^{a,b}	≥ 1500 and < 2000	1
25 - 49% ^{a,b}	≥ 1000 and < 1500	2
50 - 74% ^{a,b}	≥ 500 and < 1000	3
$> 75%$ ^{a,b}	< 500	4

- a. If at any level of decrease, the platelet count falls below $20 \times 10^9/L$, toxicity will be considered Grade 4. If the baseline platelet count is $< 20 \times 10^9/L$, platelet toxicity cannot be evaluated.
- b. Baseline and subsequent Hgb values must be determined the day of any given transfusion.
- c. If the ANC was $< 1000/\mu L$ before therapy, the patient is not evaluable for toxicity referable to the ANC.

Appendix E: EORTC QLQ-C30

EORTC QLQ-C30 (version 3)

We are interested in some things about you and your health. Please answer all of the questions yourself by circling the number that best applies to you. There are no "right" or "wrong" answers. The information that you provide will remain strictly confidential.

Please fill in your initials:

--	--	--	--	--

Your birthdate (Day, Month, Year):

--	--	--	--	--	--	--	--	--	--

Today's date (Day, Month, Year):

31

--	--	--	--	--	--	--	--	--	--

	Not at All	A Little	Quite a Bit	Very Much
1. Do you have any trouble doing strenuous activities, like carrying a heavy shopping bag or a suitcase?	1	2	3	4
2. Do you have any trouble taking a long walk?	1	2	3	4
3. Do you have any trouble taking a short walk outside of the house?	1	2	3	4
4. Do you need to stay in bed or a chair during the day?	1	2	3	4
5. Do you need help with eating, dressing, washing yourself or using the toilet?	1	2	3	4

During the past week:

	Not at All	A Little	Quite a Bit	Very Much
6. Were you limited in doing either your work or other daily activities?	1	2	3	4
7. Were you limited in pursuing your hobbies or other leisure time activities?	1	2	3	4
8. Were you short of breath?	1	2	3	4
9. Have you had pain?	1	2	3	4
10. Did you need to rest?	1	2	3	4
11. Have you had trouble sleeping?	1	2	3	4
12. Have you felt weak?	1	2	3	4
13. Have you lacked appetite?	1	2	3	4
14. Have you felt nauseated?	1	2	3	4
15. Have you vomited?	1	2	3	4

Please go on to the next page

During the past week:

	Not at All	A Little	Quite a Bit	Very Much
16. Have you been constipated?	1	2	3	4
17. Have you had diarrhea?	1	2	3	4
18. Were you tired?	1	2	3	4
19. Did pain interfere with your daily activities?	1	2	3	4
20. Have you had difficulty in concentrating on things, like reading a newspaper or watching television?	1	2	3	4
21. Did you feel tense?	1	2	3	4
22. Did you worry?	1	2	3	4
23. Did you feel irritable?	1	2	3	4
24. Did you feel depressed?	1	2	3	4
25. Have you had difficulty remembering things?	1	2	3	4
26. Has your physical condition or medical treatment interfered with your family life?	1	2	3	4
27. Has your physical condition or medical treatment interfered with your social activities?	1	2	3	4
28. Has your physical condition or medical treatment caused you financial difficulties?	1	2	3	4

For the following questions please circle the number between 1 and 7 that best applies to you

29. How would you rate your overall health during the past week?

1 2 3 4 5 6 7

Very poor

Excellent

30. How would you rate your overall quality of life during the past week?

1 2 3 4 5 6 7

Very poor

Excellent

© Copyright 1995 EORTC Quality of Life Group. All rights reserved. Version 3.0

Appendix F: EQ-5D-5L

(English version for the UK)

SAMPLE

UK (English) v. 2 © 2009 EuroQol Group. EQ-5D™ is a trade mark of the EuroQol Group

Under each heading, please tick the ONE box that best describes your health TODAY

MOBILITY

- I have no problems in walking about
- I have slight problems in walking about
- I have moderate problems in walking about
- I have severe problems in walking about
- I am unable to walk about

SELF-CARE

- I have no problems washing or dressing myself
- I have slight problems washing or dressing myself
- I have moderate problems washing or dressing myself
- I have severe problems washing or dressing myself
- I am unable to wash or dress myself

USUAL ACTIVITIES (e.g. work, study, housework, family or leisure activities)

- I have no problems doing my usual activities
- I have slight problems doing my usual activities
- I have moderate problems doing my usual activities
- I have severe problems doing my usual activities
- I am unable to do my usual activities

PAIN / DISCOMFORT

- I have no pain or discomfort
- I have slight pain or discomfort
- I have moderate pain or discomfort
- I have severe pain or discomfort
- I have extreme pain or discomfort

ANXIETY / DEPRESSION

[figure not shown]
- I am not anxious or depressed
- I am slightly anxious or depressed
- I am moderately anxious or depressed
- I am severely anxious or depressed
- I am extremely anxious or depressed

²
UK (English) v.2 © 2009 EuroQol Group. EQ-5D™ is a trade mark of the EuroQol Group

- We would like to know how good or bad your health is TODAY.
- This scale is numbered from 0 to 100.
- 100 means the best health you can imagine.
0 means the worst health you can imagine.
- Mark an X on the scale to indicate how your health is TODAY.
- Now, please write the number you marked on the scale in the box below.

YOUR HEALTH TODAY =

The best health
you can imagine

The worst health
you can imagine

3
UK (English) v.2 © 2009 EuroQol Group. EQ-5D™ is a trade mark of the EuroQol Group

Appendix G: FACiT-Fatigue

FACIT Fatigue Scale (Version 4)

Below is a list of statements that other people with your illness have said are important. Please circle or mark one number per line to indicate your response as it applies to the past 7 days.

		Not at all	A little bit	Some- what	Quite a bit	Very much
Hi7	I feel fatigued	0	1	2	3	4
Hi12	I feel weak all over	0	1	2	3	4
An1	I feel listless (“washed out”).....	0	1	2	3	4
An2	I feel tired.....	0	1	2	3	4
An3	I have trouble starting things because I am tired.....	0	1	2	3	4
An4	I have trouble finishing things because I am tired	0	1	2	3	4
An5	I have energy.....	0	1	2	3	4
An7	I am able to do my usual activities	0	1	2	3	4
An8	I need to sleep during the day	0	1	2	3	4
An12	I am too tired to eat.....	0	1	2	3	4
An14	I need help doing my usual activities	0	1	2	3	4
An15	I am frustrated by being too tired to do the things I want to do.....	0	1	2	3	4
An16	I have to limit my social activity because I am tired.....	0	1	2	3	4

Appendix H: Cumulative Illness Rating Scale (CIRS)

CIRS is an indicator of illness severity and comorbidity in older patients ([Extermann, 1998](#))¹.

CIRS scoring is to be performed in the setting of a pretreatment comprehensive history and physical by a licensed provider (nurse, PA, MD, or DO) for all patients 65 years and older.

Instructions:

The following pages include the CIRS scoring worksheet displaying 14 organ-system categories. Write brief descriptions of the medical problem(s) that justified the endorsed score on the line following each item. Circle the appropriate score from 0 – 4 based on the rating strategy. Space is provided in each system organ class to provide written descriptions.

1. Complete each category score as identified by the rating strategy on the worksheet
2. Each category has room for written comments. If additional room is needed, please document on the back of the form
3. Add the number of **Total Categories Endorsed** (measured)
4. Provide the **Total Score**
5. Provide the **Severity Index** (total score divided by total number of categories endorsed)
6. Provide the number of categories at **level 3 severity**
7. Provide the number of categories at **level 4 severity**

CLL Rating:

Please take into account that CLL/SLL diagnosis itself or induced illness or organ damage (including cytopenias) are not included in this rating scale. The goal of this rating scale is to assess comorbidity other than CLL/SLL in the patient.

¹ Extermann M, Overcash J, Lyman GH, Parr J, Balducci L, Comorbidity and functional status are independent in older patients. *J Clin Oncol* 1998; 16: 1582–87.

PCYC 1112-CA Scoring Sheet CIRS(G)

Cumulative Illness Rating Scale for Geriatrics²

Patient ID# _____ Site # _____ Investigator: _____

Rater Name: _____ Date: ___/___/___

***Note Rater must be on delegation of authority log**

Rating Strategy

Please see specific scoring guidelines below for each organ system.

0 – No Problem

1 – Current mild problem or past significant problem

2 – Moderate disability or morbidity/requires “first line” therapy

3 – Severe/constant significant disability/”uncontrollable” chronic problems

4 – Extremely severe/immediate treatment required/end organ failure/severe impairment of function

Adapted from ²Extermann M, Overcash J, Lyman GH, Parr J, Balducci L, Comorbidity and functional status are independent in older patients. J Clin Oncol 1998; 16: 1582–87.

ORGAN SYSTEM	IF IMPAIRMENT, SPECIFY	SCORE
HEART		0 1 2 3 4
VASCULAR		0 1 2 3 4
HEMATOPOETIC		0 1 2 3 4
RESPIRATORY		0 1 2 3 4
ENT/LARYNX		0 1 2 3 4
UPPER GI		0 1 2 3 4
LOWER GI		0 1 2 3 4
LIVER		0 1 2 3 4
RENAL		0 1 2 3 4
GU		0 1 2 3 4
MUSCULOSKELETAL/INTEGUMENT		0 1 2 3 4
NEUROLOGICAL		0 1 2 3 4
ENDOCRINE/METABOLIC/BREAST		0 1 2 3 4
Calculated Ratings		
Total Number Categories Endorsed (this is the number of categories above that have a score >0)		
Total Score (this is the sum of the individual scores above)		
Severity Index (total score/total number of categories endorsed)		
Number of Categories at level 3 severity (this is the number of categories above that have a score of 3)		
Number of Categories at level 4 severity (this is the number of categories above that have a score of 4)		

Appendix I: Rai & Binet Staging

Rai Stage	Binet* Stage
0 Lymphocytes (L) in blood ($>5000/\mu\text{L}$)	A <3 sites involved, Hgb ≥ 10 g/dL, platelets $\geq 100,000/\mu\text{L}$
I L + enlarged lymph nodes (LN)	
II L + spleen and/or liver (LN positive or negative)	B ≥ 3 sites involved, Hgb ≥ 10 g/dL, platelets $\geq 100,000/\mu\text{L}$
III L + anemia (Hgb < 11 g/dL)	C Hgb < 10 g/dL or platelets $< 100,000/\mu\text{L}$
IV L + thrombocytopenia (platelets $< 100,000/\mu\text{L}$)	

*Involved sites are liver, spleen, and lymph nodes in inguinal, auxiliary, and cervical regions.

Appendix J: New York Heart Association Functional Classification

Class	Functional Capacity: How a patient with cardiac disease feels during physical activity
I	Patients with cardiac disease but resulting in no limitation of physical activity. Ordinary physical activity does not cause undue fatigue, palpitation, dyspnea or anginal pain.
II	Patients with cardiac disease resulting in slight limitation of physical activity. They are comfortable at rest. Ordinary physical activity results in fatigue, palpitation, dyspnea or anginal pain.
III	Patients with cardiac disease resulting in marked limitation of physical activity. They are comfortable at rest. Less than ordinary activity causes fatigue, palpitation, dyspnea or anginal pain.
IV	Patients with cardiac disease resulting in inability to carry on any physical activity without discomfort. Symptoms of heart failure or the anginal syndrome may be present even at rest. If any physical activity is undertaken, discomfort increases.
Class	Objective Assessment
A	No objective evidence of cardiovascular disease. No symptoms and no limitation in ordinary physical activity.
B	Objective evidence of minimal cardiovascular disease. Mild symptoms and slight limitation during ordinary activity. Comfortable at rest.
C	Objective evidence of moderately severe cardiovascular disease. Marked limitation in activity due to symptoms, even during less-than-ordinary activity. Comfortable only at rest.
D	Objective evidence of severe cardiovascular disease. Severe limitations. Experiences symptoms even while at rest.

Appendix K: Definitions for PCYC-1112-CA Eligibility Criteria

Chemoimmuno-therapy	For the purpose of this protocol, a combination treatment regimen that contains both a cytotoxic, specifically a purine analog or alkylating agent, chemotherapy agent and an anti-CD20 monoclonal antibody (eg, rituximab) administered together.
Autoimmune hemolytic anemia (AIHA)	Defined by at least one marker of hemolysis (indirect bilirubin above the upper limit of normal (ULN) not due to liver disease, increased lactate dehydrogenase (above ULN) without alternative etiology, or increased absolute reticulocytosis (above ULN) or bone marrow erythropoiesis in the absence of bleeding) AND at least one marker of direct or indirect autoimmune mechanism (positive direct antiglobulin for IgG or C3d, cold agglutinins) (Ding 2007).
Immune thrombocytopenia (ITP)	Immune thrombocytopenia is defined by platelets $\leq 100,000/\mu\text{L}$ and increased megakaryocytes on the bone marrow exam.
Autoimmune cytopenia poorly responsive to therapy	Autoimmune anemia or thrombocytopenia poorly responsive to treatment includes those patients with recurrent autoimmune cytopenias, those receiving low dose steroids (≤ 20 mg of prednisone or equivalent) and those on intravenous immune globulin (IVIG). Patients receiving higher doses of steroids or experiencing declining platelets or hemoglobin due to autoimmune destruction during the 4 weeks prior to the first dose of study drug are considered for the purposes of this protocol to have uncontrolled autoimmune cytopenias (as defined below) and are not eligible for enrollment.
Autoimmune cytopenia, uncontrolled	Uncontrolled autoimmune anemia or thrombocytopenia is defined as those patients receiving > 20 mg prednisone (or equivalent) daily or have declining platelets or hemoglobin due to autoimmune destruction during the 4 weeks prior to the first dose of study drug.

Appendix L: Child-Pugh Score for Subjects with Liver Impairment

Measure	1 point	2 points	3 points
Total bilirubin, $\mu\text{mol/L}$ (mg/dL)	<34 (<2)	34-50 (2-3)	>50 (>3)
Serum albumin, g/L (g/dL)	>35 (>3.5)	28-35 (2.8-3.5)	<28 (<2.8)
PT/INR	<1.7	1.71-2.30	>2.30
Ascites	None	Mild	Moderate to Severe
Hepatic encephalopathy	None	Grade I-II (or suppressed with medication)	Grade III-IV (or refractory)

Points	Class
5-6	A
7-9	B
10-15	C

Source:

Appendix M: Schedule of Assessments for Patients Treated with Ofatumumab who are to Receive Next-line Ibrutinib Therapy

Study Weeks	Assessment for Next-line Ibrutinib Therapy	Treatment Phase			Follow-up Phase
		Every 4 weeks for 24 weeks	Every 12 weeks until PD	End-of-Treatment Visit	Follow-up (Every 12 weeks)
Study Windows	±14 d	±7 d	±7 d	30 (±3 d)	±7 d
Study Drug Administration					
Ibrutinib 420 mg per day PO		Continuous Daily Dosing			
Procedures					
Medical Monitor approval	X				
Concomitant medications	X	X	X	X	
Adverse events		X	X	X	
Physical examination, vital signs, ECOG	X	X	X	X	
Hematology	X	X ^e	X	X	
Serum chemistry	X				
PK sampling if on CYP3A4/5 inhibitors ^d					
Disease assessment:					
Investigator assessment of response and for progression ^a			X		
Predictive biomarkers			X ^b		
Survival status					X ^c
Subsequent anticancer therapies					X ^c

CLL=chronic lymphocytic leukemia; d=day; ECOG=Eastern Cooperative Oncology Group; IRC=Independent Review Committee; PD=progressive disease; PO=oral; qd=once daily

- a. Efficacy assessments should include CT scan annually until the first disease progression on protocol. For patients who have had experienced PD and are crossed over to ibrutinib, CT scans for response assessments may be performed at investigator's discretion.
- b. Blood samples will be collected at Week 12 Day 1 and at PD
- c. By telephone
- d. Patients who must take strong or moderate CYP3A4/5 inhibitors while on treatment with ibrutinib, additional PK collections for evaluation of ibrutinib exposure is requested at the following scheduled visit after concomitant CYP3A4/5 inhibitor has started and still in use. Please refer to [Section 7.1.21](#) for the PK collection schedules.
- e. CBC should be performed weekly for the first 4 weeks

## LIST OF ABBREVIATIONS

CI	confidence interval
CLL	chronic lymphocytic leukemia
CMH	Cochran-Mantel-Haenszel
CR	complete response
CRi	complete response with incomplete marrow recovery
CSR	Clinical Study Report
CTCAE	Common Terminology Criteria for Adverse Events
del17p	deletion of the short arm of chromosome 17
DMC	data monitoring committee
HR	hazard ratio
IRC	independent review committee
ITT	intent to treat
iwCLL	International Workshop on CLL
KM	Kaplan-Meier
MedDRA	Medical Dictionary for Regulatory Activities
NCI	National Cancer Institute
nPR	nodular partial response
ORR	overall response rate
OS	overall survival
PD	progressive disease
PFS	progression-free survival
PR	partial response
SAE	Serious adverse events
SAP	statistical analysis plan
SLL	small lymphocytic lymphoma
TEAE	Treatment-emergent adverse events

## **1. INTRODUCTION**

Study PCYC-1112-CA (hereafter referred to as Study 1112) is a randomized, multicenter, open-label, comparator-controlled Phase 3 study of ibrutinib versus ofatumumab in subjects with previously treated chronic lymphocytic leukemia (CLL)/small lymphocytic lymphoma (SLL). Study 1112 compared the efficacy and safety of orally administered ibrutinib 420 mg/day with that of ofatumumab administered intravenously at an initial dose of 300 mg followed by 2000 mg x 11 doses over a 24-week period. Randomization of subjects into both treatment arms was 1:1, and subjects received ibrutinib until progressive disease (PD) or unacceptable toxicity was observed, whichever occurred first. Two separate randomization schemes were generated for each geographic region (North America vs. Rest of World). Under each scheme, randomization was stratified using the following factors:

- Presence vs. absence of disease refractory to purine analog and anti-CD20 containing combination chemo-immunotherapy regimen.
- Presence vs. absence of deletion of the short arm of chromosome 17 (del17p), as defined by assay specification on pre-treatment fluorescence in situ hybridization or cytogenetics evaluation.

The primary endpoint was progression-free survival (PFS) as assessed by the independent review committee (IRC) per criteria from the 2008 International Workshop on CLL (iwCLL) with the clarification regarding treatment-related lymphocytosis (Hallek et al, 2013). Key secondary efficacy endpoints included overall survival (OS) and overall response rate (ORR) (based on the IRC assessment).

Initially, subjects treated with ofatumumab who had experienced PD as confirmed by an IRC were allowed to receive ibrutinib if deemed appropriate by the investigator following medical monitor approval. Based on the positive results from the interim analysis in December 2013, the data monitoring committee (DMC) recommended to allow the remaining subjects originally randomized to ofatumumab to be provided with access to ibrutinib therapy. In addition, the DMC recommended the interim analysis be the primary analysis for the study and the Clinical Study

Report (CSR) was completed on 25 March 2014. After the primary analysis, IRC evaluations were discontinued, while efficacy assessments by the investigators continued until study closure.

Subjects remaining on treatment at the time of study closure will have the option to be rolled over to a separate long-term extension study.

The final analysis will be based on the final data extract from 26 November 2018. This statistical analysis plan (SAP) is to describe the final analysis of data in evaluation of efficacy and safety of Study 1112.

## **2. GENERAL ANALYSIS CONSIDERATION**

### **2.1. ITT Population**

The Intent-to-Treat (ITT) population includes all randomized subjects. Subjects in this population will be analyzed according to the treatment to which they were randomized. The ITT population will be used for efficacy analyses and to produce subject disposition summaries.

### **2.2. Safety Population**

All randomized subjects who received at least one dose of study drug will be included in the safety population. Subjects in the safety population will be analyzed according to the actual treatment received and will be used to summarize the safety (including dosing) data.

## **3. SUBJECT INFORMATION**

### **3.1. Duration of Study Follow-up**

Duration of follow-up on the study will be summarized by treatment arm and for the combined arms. Median duration will be obtained using Kaplan–Meier methodology with reverse censoring.

#### 4. EFFICACY ANALYSES

Analysis of endpoints will be conducted on the ITT population, unless otherwise specified. Table 1 summarizes the efficacy endpoints and analysis methods to be performed.

The two randomization stratification factors will be used for the stratified analysis/test.

Table 1: Definitions and Analyses for Endpoints

Endpoint	Definition	Analysis Method
Progression-free survival (PFS) per investigator	Time from date of randomization to date of first documentation of PD per investigator response assessment or date of death due to any cause, whichever occurs first, regardless of the use of subsequent anticancer therapy including crossover prior to documented PD or death. Subjects who are alive and had not progressed will be censored at the date of last evidence of non-PD.  Subjects without a baseline assessment or adequate post baseline assessment will be censored at date of randomization.	Kaplan-Meier (KM) will be used to estimate median with its 95% confidence interval (CI) and selected landmark estimates (95% CI). The hazard ratio (HR) with its 95% CI, will be estimated by Cox regression model (with treatment as the only covariate) stratified by the two randomization stratification factors. KM curves and the forest plot of HRs for PFS in each subgroup will be provided.
Overall survival (OS)	Time from date of randomization to date of death from any cause. Subjects who are known to be alive or whose survival status is unknown will be censored at the date when they were last known to be alive.  Subjects who received subsequent anti-neoplastic therapy will not be censored at next-line therapy, including ofatumumab subjects who received ibrutinib as subsequent therapy.	ITT analysis: The same methods used to analyze PFS will be used to analyze OS.
Overall response rate (ORR) per investigator	The proportion of subjects achieving a best overall response of CR, CRi, nPR, or PR per investigator assessment at or prior to initiation of subsequent anti-neoplastic therapy.	P-value is based on Cochran-Mantel-Haenszel (CMH) chi-square test stratified by the two randomization stratification factors.
Sustained hemoglobin improvement	Proportion of subjects with hemoglobin increase $\geq 20$ g/L over baseline continuously for $\geq 56$ days without blood transfusions or growth factors.	Analysis for ITT and the subgroup with anemia at baseline (hemoglobin $\leq 110$ g/L): Chi-square test.
Sustained platelet improvement	Proportion of subjects with platelet increase $\geq 50\%$ over baseline continuously for $\geq 56$ days without blood transfusions or growth factors.	Analysis for ITT and the subgroup with thrombocytopenia at baseline (platelet $\leq 100 \times 10^9$ /L): Chi-square test.

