7.3.3. Follow-up Phase

7.3.3.1. Post-treatment Phase

After discontinuation of treatment, the following assessments will be performed every 12 weeks (± 7 days) until disease progression or study closure, whichever is earlier:

- Subsequent anticancer therapies
- Physical examination and ECOG performance status
- Disease-related symptoms (no longer required per Amendment 5)
- MRU (no longer required per Amendment 5)
- PRO assessments
- Hematology
- Serum immunoglobulins and β_2 -microglobulin
- T/B/NK cells
- Flow cytometry-based immunophenotype assays
- Predictive biomarkers and mechanisms of resistance

Prior to disease progression, response assessment (including CT, CBC and PE) need to be continued on a calendar schedule even if the patient receives subsequent anticancer therapy.

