7.3.3.2. Post-disease Progression Phase

Once patient progresses, the following assessments will be assessed every 12 weeks until death, withdrawal by patient, lost to follow-up, or study terminated by Sponsor, whichever comes first.

- Subsequent anticancer therapies
- MRU (no longer required per Amendment 5)
- Survival status

- Occurrence of any additional malignancy
- Occurrence of transformation to a more aggressive histology (Richter's transformation)

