12.8.2.4. Hematological Improvements

In the subset of patients with cytopenia(s) at baseline (Hgb ≤ 11 g/dL, platelets $\leq 100,000/\mu\text{L}$, or ANC $\leq 1500/\mu\text{L}$), time to sustained improvement and percentage of patients with sustained hematological improvement will be measured. Sustained hematological improvement is defined as improvement in cytopenia by $\geq 50\%$, or Hgb > 11 g/dL, ANC $> 1500/\mu\text{L}$, platelets $> 100,000/\mu\text{L}$ with the duration of improvement lasting for at least 2 months without blood transfusion or growth factors.

- Time to sustained improvement in blood count will be compared using unstratified log rank test. The distribution of the time to sustained improvement will be summarized using Kaplan-Meier estimates.
- Percentage of patients with sustained improvement will be compared using χ^2 test.

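### SAP Table 1 tests haemoglobin and platelet improvement as untimed proportions, with no data cut and without the protocol's time-to-improvement test, so the result depends on unequal observation and on whether crossover counts are used

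*SAP*

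**What the plan says.** SAP section 4, Table 1, defines each endpoint as the proportion of subjects whose haemoglobin (or platelets) rises by a set amount and stays there for at least 56 days without transfusion or growth factors. The test is a chi-square in two populations: "Analysis for ITT and the subgroup with anemia at baseline" and, for platelets, "Analysis for ITT and the subgroup with thrombocytopenia at baseline". Neither row states a window, a censoring rule or a cut-off at a new therapy.

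Other rows of the same table do deal with this. ORR counts only responses "at or prior to initiation of subsequent anti-neoplastic therapy". PFS and OS are censored time-to-event analyses, and both say that later therapy, including crossover, is disregarded.

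Protocol 12.8.2.4 has two analyses of haematological improvement: a chi-square on the percentage, and a second one: "Time to sustained improvement in blood count will be compared using unstratified log rank test". Only the chi-square is in the SAP.

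On when counts are taken:
- **Before progression.** Protocol 7.3.3.1 schedules haematology after treatment ends "until disease progression or study closure, whichever is earlier". The same section keeps the response-assessment blood counts going before progression even if another anticancer therapy has started.
- **After progression.** The list in protocol 7.3.3.2 and the matching column of Appendix A contain no haematology.
- **After crossover.** Appendix M restarts haematology for ofatumumab patients who take ibrutinib: "CBC should be performed weekly for the first 4 weeks", then every 4 weeks to week 24 and every 12 weeks until progression.

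**The concern.** A proportion without a time limit mixes how fast patients improve with how long they are watched. PFS differs between the arms (protocol 7.3.4 records that the primary endpoint was met), so scheduled observation before progression differs too. After the interim analysis the DMC also "recommended to allow the remaining subjects originally randomized to ofatumumab to be provided with access to ibrutinib therapy". For control patients who had not progressed, that ends observation on ofatumumab alone for a reason unrelated to the drug.

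The SAP does not say which counts enter the proportion, and the two possible choices distort it in different ways. A significant result could be read as a haematological benefit separate from PFS when the analysis cannot distinguish the two. The protocol's companion analysis, which allows for unequal observation, would have helped and is missing.

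**Working it through.** **The plan's own figure.** No power is stated for the blood-count tests. The only sizing figure is about 90% power for PFS with 176 events at hazard ratio 0.6 (protocol 12.3). Schoenfeld: |ln 0.6|/2 × √176 = 0.2554 × 13.27 = 3.39, and 3.39 − 1.96 = 1.43, which gives 92.3%. With the O'Brien-Fleming interim at 117/176 events and the futility bound obeyed, it is 90.7% (Schoenfeld) or 89.8% (Freedman). The figure reproduces, so hazard ratio 0.6 is a fair lower reference for the PFS difference.

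**Inputs from the documents.** 175 per arm (minimum 350, 1:1). Control median PFS 5.8 months, between the 5.7 and 5.9 in protocol 2.2. Ibrutinib PFS either at hazard ratio 0.6 or at the 88% 12-month rate in protocol 1.3.2.1. Follow-up capped at 60 months in the simulations.

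**Assumptions not in the documents.** Exponential times; a share q of patients able to improve; the same improvement rate λ in both arms; 80 per arm for a cytopenic subgroup; the crossover share.

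**Case 1: counts stop at progression.** With progression/death hazard μ, and 56 days = 1.84 months,

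P(improved) = q × λ/(λ+μ) × exp(−1.84 μ).

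Control μ = ln 2/5.8 = 0.1195 per month. Ibrutinib μ = 0.6 × 0.1195 = 0.0717, or −ln(0.88)/12 = 0.0107.

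Example with q = 0.6 and median time to improvement 4 months (λ = 0.1733):
- Control: 0.6 × 0.592 × 0.803 = 28.5%.
- Ibrutinib, hazard ratio 0.6: 0.6 × 0.707 × 0.876 = 37.2%.
- Ibrutinib, 88%: 0.6 × 0.942 × 0.981 = 55.4%.

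The chi-square rejects 41% of the time for 28.5% v 37.2% with 175 per arm (21% with 80), and 100% for 28.5% v 55.4% (94% with 80). The improvement rate is identical in both arms.

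Over medians of 1 to 24 months with 175 per arm, the closed form gives:

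| Share able to improve | Hazard ratio 0.6 | 88% at 12 months |
|---|---|---|
| q = 0.6 | 23-45% | 89-100% |
| q = 1 | 60-79% | 100% |

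Simulation on the protocol's visit schedule gives 39-73% and 99-100% with 175 per arm, and 20-44% and 85-100% with 80. When PFS is set equal, the chi-square returns to 5.3-5.6%, so the PFS difference is the cause. A log-rank on time to improvement, censored at the last count, rejects 4-6.5% in the same runs.

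**Case 2: counts after crossover included.** Simulation with q = 0.6, median 3 months, 175 per arm, crossover at progression and the same improvement rate throughout:

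| Share crossing over | Ibrutinib PFS | Control v ibrutinib improved | Chi-square rejects |
|---|---|---|---|
| 0% | HR 0.6 | 28% v 37% | 42% |
| 60% | HR 0.6 | 42% v 37% | 13% |
| 90% | HR 0.6 | 49% v 37% | 55%, favouring control |
| 0% | 88% | 29% v 56% | 100% |
| 60% | 88% | 47% v 56% | 40% |
| 90% | 88% | 55% v 56% | 5% |

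The same data can point either way, depending on a choice that the SAP does not state.

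**How safe is the log-rank?** The 4-6.5% depends on improvement and progression being independent. Protocol 8.4.7 makes a CLL-related fall in haemoglobin or platelets a form of progression, so independence is doubtful. Adding an assumed shared gamma frailty of variance 0.5 (fast progressors improve slowly, same distribution in both arms), the log-rank rejects 7-11% at hazard ratio 0.6 and 19-43% at 88%, against ibrutinib. The chi-square remains inflated (28-49% and 100%).

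**The case against.** The percentage with sustained improvement is a protocol endpoint in its own right, and the chi-square is its protocol-specified test. It is valid for equal cumulative proportions, and a patient who progresses before improving can fairly count as a failure. The ORR comparison has the same structure. This stands: the inflation above is relative to a null of equal improvement rates, and it is no reason to remove the test.

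A reader might infer that blood counts end at progression, so the test is biased towards ibrutinib by an amount that grows with follow-up. The documents do not support that. Appendix M restarts counts on crossover ibrutinib and Table 1 has no cut, so the direction is open. A reader might also infer that the log-rank should replace the chi-square. The frailty result shows that it has its own bias, in the opposite direction.

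The magnitudes are soft. Control PFS comes from a fludarabine-refractory population, narrower than this trial's eligibility; the 88% comes from an earlier study; no improvement rate is documented. Finally, the primary analysis and its report date from 2014, and the SAP names OS and ORR as the key secondary endpoints. Time to improvement may have been reported then; the documents do not say. None of this supplies the missing cut or companion test in the final analysis.

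**Conclusion.** The point holds as an unstated data cut together with an omitted companion analysis. If counts stop at progression, the chi-square can reject far above 5% under equal improvement rates: about 30-70% at hazard ratio 0.6 and close to 100% at 88% 12-month PFS, with 175 per arm. If crossover counts are included, the comparison is no longer ibrutinib against ofatumumab, and the excess may disappear or favour control. The mechanism follows from the documents. The sizes rest on assumed improvement rates, exponential times and a historical control PFS, and are illustrative. The chi-square is not invalid and no pro-ibrutinib bias has been demonstrated. Secondary endpoints are affected; the primary PFS conclusion is not.

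**What to change.** In SAP Table 1, for both blood-count rows:

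1. Count only improvement at or before the start of subsequent anti-neoplastic therapy, including crossover ibrutinib, as the ORR row does. State whether the 56 days must be complete by then; the calculation above requires it before progression.
2. Keep the percentage and its chi-square, labelled as a comparison of cumulative proportions improving before progression or next-line therapy. Show haematology observation time per arm beside it.
3. Restore the protocol's log-rank test of time to sustained improvement, censored at the last count before progression or next-line therapy, with cumulative incidence curves treating progression and death as competing events.
4. Note that the log-rank assumes censoring unrelated to improvement, which protocol 8.4.7 makes doubtful. Claim a separate haematological benefit only if both analyses agree.

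The cost is SAP wording and two extra outputs from data already collected. The downside is that the result may look less favourable.
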